Chief Investigator Name: [name]

Signature:

Date: 5.7.2020

4. Summary and synopsis

Short title	EPIFEVER-2
Methodology	Observational, mechanistic cohort study.
Objectives / aims	To determine whether polymorphisms in interleukin-1 receptor antagonist gene promotes fever in labouring women receiving epidural analgesia.
Number of participants	637 women
Inclusion and exclusion criteria	Women aged >18 years in active or induced labour.
Statistical methodology and analysis (if applicable)	Incidence of epidural-related maternal fever compared between IL-1ra allele scores.
Study duration	24 months

5. Introduction

5.1. Background

Epidural-related maternal fever (ERMF) occurs in 15-20% of labouring women.(Sultan et al., 2016) We have reported that the local anaesthetic agent used most commonly in epidurals – bupivacaine- reduces caspase-1 activity, resulting in lower release of the anti-pyrogenic cytokine interleukin-1 receptor antagonist (IL-1Ra) from circulating leucocytes.(Del Arroyo et al., 2019) Reduced IL1Ra secretion may promote ERMF since IL-1Ra is a potent anti-pyrogenic cytokine in active labour.(Girard et al., 2010; Kallapur et al., 2009) These data reconcile previous observations where pro-inflammatory cytokines increase during active labour yet did not differ substantially between women who develop fever versus those that do not.(Goetzl et al., 2002).

Impaired IL-1ra release may promote ERMF. IL-1Ra is a key determinant of systemic inflammation in pregnancy IL-1Ra is normally present in the circulation of healthy persons, whereas IL- α and IL-1 β are not typically detectable in the absence of inflammation or autoimmunity.(Witkin et al., 2002) IL-1Ra appears to prevent proinflammatory responses to minor nonpathogenic stimuli. IL-1Ra levels are higher in women.(Lynch et al., 1994) In pregnancy- a proinflammatory state- IL-1 β is key for the initiation of infection-related preterm labour and delivery.(Romero and Tartakovsky, 1992) In mice, the injection of IL-1Ra before IL-1 β administration prevents preterm birth.(Romero and Tartakovsky, 1992) Similarly, we found IL-1Ra/IL-1 β ratio declined 4h after epidural analgesia was instituted, consistent with a role in promoting ERMF.(Del Arroyo et al., 2019)

Genetic determinants of IL-1Ra levels impact on outcomes in pregnancy The gene coding for IL-1ra is polymorphic due to an 86-bp tandem repeat sequence of variable length.(Tarlow et al., 1993) Most individuals are homozygous for IL-1RN*1 (four repeat sequences), which is more common than IL-1RN*1/IL-1RN*2 heterozygotes. Plasma IL-1ra levels are 'dosedependently' higher in individuals with increasing number of repeats.(Interleukin 1 Genetics, 2015) For example, median vaginal IL1-Ra levels are ~3-fold higher in women with the IL-1RN*2 variant.(Barton et al., 2003; Jeremias et al., 1999) IL-1Ra gene polymorphisms resulting in lower IL-1Ra/IL-1 β ratios are associated with an increased risk of preterm birth.(Nadeau-Vallee et al., 2016)

5.2. Rationale

Thus, we propose that ERMF is driven by the relative lack of an anti-pyrogenic cytokine that suppresses fever. To establish the clinical relevance of these findings, we propose to employ a genomic approach at the population level to confirm the link between ERMF and IL-1Ra. This complementary approach examines the relationship between genetic variants known to result in higher circulating levels of IL1Ra.(Herder et al., 2017)

5.3. Risks / benefits

There are no study specific risks, as blood samples are obtained as part of routine care.

6. Study objectives

6.1. Primary objective

To demonstrate that single nucleotide polymorphisms in the gene encoding for IL-1Ra are associated with higher risk of ERMF defined as maternal pyrexia (defined as a temperature >38.0 °C once, or 37.5 °C on two occasions ≤ 2 hours apart) during active labour before delivery. (DeArroyo et al., 2019; Lange et al 2017; Royal College of Obstetricians Green-top Guideline No. 64a).

6.2. Secondary objectives

1. Clinical outcomes for mother and baby.
2. To examine ex-vivo whether local anaesthetics and/or labour analgesics vary in their ability to inhibit IL-1Ra release, and hence ERMF.
3. Post-hoc identification of novel immune-related single nucleotide polymorphisms and/or RNA changes associated with ERMF.

[figure not shown]
6.3. Primary endpoint

The primary endpoint is maternal temperature $>38^{\circ}\text{C}$ ≥ 4 h after epidural analgesia is commenced and/or prescription of antibiotics during labour before delivery (triggered by RCOG guidelines for two temperatures $>37.5^{\circ}\text{C}$). Hourly temperature logs kept by midwives as part of routine care for women receiving epidural analgesia.

6.4. Secondary endpoints

Prescription of antibiotics during labour, obstetric intervention, mode of delivery, complications and level of clinical care required for mother and baby will be recorded from electronic and/or drug charts. Laboratory-based measures of genomic and proteomic signatures associated with developing fever after epidural insertion.

6.5. Study Scheme Diagram

7. Subject population

7.1. *Inclusion criteria*

- ≥18 yr old females of any gestational age,
- Singleton or twin pregnancy,
- requesting an epidural for labour analgesia.

7.2. *Exclusion criteria*

- Unwilling or unable to give consent
- Refusal of consent for competent participants,
- Inability to understand written and/ or verbal English
- immune/genetic syndromes/mutations,
- microbiologically proven infection prior to epidural insertion,
- established pyrexia
- intrauterine death.

8. Study Design

This is an observational mechanistic cohort study in which the development of fever after epidural analgesia and/or antibiotic prescription will be correlated with an allele score generated by the presence/absence of polymorphisms in the IL-1Ra gene. The primary clinical outcome is masked to genomic analyses. 637 women in active labour or commencing induction of labour will be studied. Participants will be selected for the study from antenatal clinics and/or following admission to labour ward. Participants will be informed about the study by their obstetric and/or anaesthetic team. No vulnerable groups will be included. Duration of participation will be from epidural insertion until birth of the baby.

9. Study procedures

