10.1. Sample size

Based on the IL-1Ra Consortium score (Interleukin 1 Genetics, 2015), women with low IL-1Ra secretion associated with an allele score 0 comprise ~12% of the population. We hypothesise that these women are more likely to sustain ERMF or be prescribed antibiotics for >2 temperatures >37.5°C over a two-hour period, compared to women with higher IL-1Ra secretion (allele score ≥ 1). The overall incidence of ERMF in EPIFEVER was 13.4% (probably an underestimate with broader inclusion criteria and lower temperature threshold for antibiotic use, as per RCOG guidelines). If individuals with an allele score 0 are more likely to develop ERMF (~22%), compared with women with IL-1Ra allele scores ≥ 1 , at least 637 women will be

required to detect an absolute difference in primary outcome of ~13%, assuming 9% incidence in women with allele scores ≥ 1 ($\alpha=0.05$; $1-\beta=0.2$).

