11.1. Source data

Hourly temperature logs kept by midwives as part of routine care for women receiving epidural analgesia. Prescription of antibiotics during labour, obstetric intervention, mode of delivery, complications and level of clinical care required for mother and baby will be recorded from electronic and/or drug charts. Laboratory-based measures of genomic and proteomic signatures associated with developing fever after epidural insertion.

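### The primary endpoint ties only its >38 °C limb to the epidural; the antibiotic limb has no epidural window and no stated check against the temperature log

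*Protocol*

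**What the plan says.** The protocol describes the outcome in several places:

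- **6.1 Primary objective.** Pyrexia is one temperature above 38.0 °C, or "37.5 °C on two occasions ≤ 2 hours apart) during active labour before delivery". There is no epidural time limit, and no prescription is needed.
- **6.3 Primary endpoint.** A temperature above 38 °C "≥ 4 h after epidural analgesia is commenced and/or prescription of antibiotics during labour before delivery". The second limb carries a temperature trigger: "prescription of antibiotics during labour before delivery (triggered by RCOG guidelines for two temperatures" above 37.5 °C.
- **10.1 Sample size.** Women with allele score 0 are expected to be more likely to have ERMF or to "be prescribed antibiotics for >2 temperatures >37.5°C over a two-hour period".
- **8 Study Design.** The "development of fever after epidural analgesia and/or antibiotic prescription will be correlated with an allele score". The trigger is absent.
- **9.3 Blinding.** Refers to temperature or antibiotic prescription, again without the trigger.
- **6.4 and 11.1.** The item collected is any prescription in labour: "Prescription of antibiotics during labour, obstetric intervention, mode of delivery, complications and level of clinical care required for mother and baby will be recorded". The source is electronic or drug charts. Temperatures come from the midwives' hourly logs.

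Two other provisions bear on timing. Section 7.2 excludes infection proven by microbiology before the epidural, and established pyrexia, which it does not define. Section 8 sets participation from insertion of the epidural to birth.

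**The concern.** The outcome is meant to be fever related to the epidural. One limb is held to a window that starts 4 h after the epidural begins; the other is held only to labour. The two limbs of one composite therefore apply different standards to the same early hours.

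The antibiotic limb also depends on a prescriber acting. Two women with identical temperature logs can be classified differently because one received a new prescription and the other did not.

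Finally, the limb is defined by its temperature trigger in 6.3 and 10.1, but Section 8 leaves the trigger out, and the data item named in 6.4 and 11.1 does not carry it. Whoever derives the endpoint from the charts has no stated rule for deciding which prescriptions qualify. At stake is outcome misclassification in the primary comparison of allele score 0 with ≥1.

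**Working it through.** The plan gives no figure on this point to reproduce. The 637 in 10.1 rests on event rates for the whole primary outcome and does not test it. The check is to run example women through the definitions as written.

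| Example | 6.1 | 6.3 | Section 8, literally |
|---|---|---|---|
| A. 37.6 °C once before and once after the epidural, ≤2 h apart; antibiotics prescribed for these readings | Pyrexia, if in active labour | Case | Case |
| B. 37.6 °C twice, both soon after the epidural; antibiotics prescribed for these readings | Pyrexia | Case | Case |
| C. 38.1 °C one hour after the epidural, no other raised reading, no prescription | Pyrexia | Not a case | Case, if the reading is fever |
| D. 37.6 °C twice, ≤2 h apart, both beyond 4 h; no new prescription (for example, already on antibiotics) | Pyrexia | Not a case | Depends on how fever is defined |
| E. No raised reading; antibiotics for another reason | No pyrexia | Not a case | Case |

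**Timing (A and B against C).** The 4 h limit attaches to the temperature limb, so 6.3 counts the lower early temperature and not the higher one. A passes the exclusions on the 6.1 definition, because a single reading of 37.6 °C is not pyrexia there.

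**Dependence on a prescription (D).** D meets 6.1 but not 6.3.

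**Missing trigger (E).** E separates 6.3 from Section 8. Applying 6.3 needs the indication, or a check against the log; neither is stated.

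**Reading count.** 6.1 asks for two readings at 37.5 °C, 6.3 for two above it, and 10.1, read literally, for more than two. A and B meet the first two but not the third.

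**Direction of the effect.** Let p0 and p1 be the event rates for allele scores 0 and ≥1, and let q be the share of true non-cases wrongly counted, equal in both groups. Then:

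- observed rate = p + (1 − p)q
- observed difference = (p0 − p1)(1 − q)
- observed risk ratio = [p0 + (1 − p0)q] / [p1 + (1 − p1)q], which moves toward 1 as q rises

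The documents do not give q. Purely to show direction, with the 22% and 9% of 10.1:

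| Assumed q | Rates | Risk ratio |
|---|---|---|
| 0 | 22.0% v 9.0% | 2.44 |
| 2% | 23.6% v 10.8% | 2.18 |
| 5% | 25.9% v 13.6% | 1.91 |
| 10% | 29.8% v 18.1% | 1.65 |

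These are not estimates. Section 10.1 states 22% and 9% for the primary outcome as a whole, so they may already include such cases.

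Missed cases such as D act differently. If a share s of true cases is captured in both groups, the ratio is s·p0 / (s·p1) = p0/p1. The ratio is unchanged, but events are lost.

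**The case against.** The strongest reply is that 6.3 governs the endpoint, and it limits the limb to temperature-triggered antibiotics; 10.1 repeats a temperature indication. Section 8 is a summary and 9.3 concerns masking. This stands, and it disposes of four stronger readings that a reader might infer:

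- **That prophylaxis or another non-fever indication makes an afebrile woman a case.** Under 6.3 it does not. Only the literal wording of Section 8 would allow it.
- **That a woman already on antibiotics can never register a later fever.** The >38 °C limb still captures her from 4 h. Only the lower-threshold fever is at risk of being missed.
- **That a stated amount of power is lost.** This needs q, which the documents do not give, and risks double counting for the reason given with the table of rates. No power figure is offered here.
- **That some cases precede the exposure.** The comparison is by genotype, which is fixed before labour. Such cases can precede the epidural, not the exposure being compared.

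A second reply is that participation starts at epidural insertion, that established pyrexia is excluded, and that the logs are described for women receiving epidurals, so readings before insertion may be uncommon in the data. This narrows the gap without closing it: none of these provisions sets a window for the antibiotic limb, and example B arises wholly after insertion.

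A third reply is that 6.4 and 11.1 name data headings rather than CRF fields, and that charts may show start times. That is fair. The point is not that the rule cannot be applied, but that the protocol does not require the check or the items needed for it.

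**Conclusion.** The point holds as a weakness in the endpoint definition that is cheap to repair. The epidural time limit covers one limb only. The temperature trigger is present in 6.3 and 10.1 and absent from Sections 8 and 9.3. No check of indication or start time is stated. Low-grade fever without a new prescription is not counted, although 6.1 would call it pyrexia.

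The size cannot be stated, because the documents give no rate of unrelated or pre-epidural antibiotics. The direction can be: false cases that occur independently of genotype move the risk ratio toward 1. That independence is an assumption. Section 5.1 links IL-1Ra polymorphisms to preterm birth, and 7.1 admits any gestational age, so the documents do not guarantee it.

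**What to change.** Reconcile 6.1, 6.3, 8, 9.3 and 10.1 on one outcome definition for analysis, including the number of readings and the threshold. Then:

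1. State an epidural-anchored window for both limbs.
2. Establish the lower-threshold component from the hourly log, using the protocol's own two-reading rule with both readings after the epidural starts.
3. Count an antibiotic prescription only if it was first started after the epidural and those logged readings support it. Record its start time and indication.
4. Classify women already on antibiotics at insertion by temperature.
5. Keep any-antibiotic prescription as a secondary endpoint, as in 6.4.

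This concerns outcome classification only and changes no care. Whether antibiotics should leave the primary endpoint altogether is open to debate, and the fix does not require it. The cost is protocol and CRF wording and minor extra abstraction from logs and charts that are already named as sources. The event count may differ somewhat from that under the present wording, so the rates assumed in 10.1 should be confirmed against the reconciled definition.

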9.1. Screening procedures

Pregnant women scheduled for hospital birth will be recruited from Barts Health NHS Trust clinical sites by their surgical team. First approach to the patient will be made by a member of the direct clinical care team. For example, they can identify and provide the PIS to the patient, after which a trained member of the research team can approach with patient with the ICF.

After identification of eligibility, a trained member of the research team will seek patients and provide patient information sheets. Potential participants will be screened to determine whether patients meet inclusion and exclusion criteria (see eligibility above).

9.2. Informed Consent Procedures

Written informed consent will be obtained from research participants by an appropriately trained researcher in a face to face setting either at Barts Health NHS Trust clinical sites or the William Harvey Research Institute. This may occur in antenatal clinic, or on labour ward at the time of request for epidural analgesia.

9.3. Blinding and procedures to minimise bias

Both primary and secondary outcomes will be analysed by individuals masked to temperature or antibiotic prescription by women during labour.

9.4. Participant recruitment schedule

Potential participants will be given the PIS for at least 1 week before deciding whether they wish to participate. If they do, they will then be consented pre-surgery by a trained member of the research team.

9.5. Criteria for Discontinuation

Patient removal of consent is the only criteria for discontinuing the study.

9.6. Procedure for Collecting Data including Case Report Forms (CRFs) and storage

All samples to be processed in the laboratory will be linked anonymised with a unique identification number (UIN). All data will be stored in password restricted computer facilities in the William Harvey Research Centre at QMUL and hard paper copy in the study master file under the custody of the CI. Research data and samples will be stored for 20 years in accordance in accordance with the Research Governance Framework and Barts Health NHS Trust Policy.

9.7. Follow-up Procedures

There only follow-up procedures after the blood sample is obtained will be to record the way the baby was delivered and whether the mother/baby needed to be treated with antibiotics.

9.8. Subject withdrawal

The participant will be informed that their involvement is completely voluntary and that they may stop participation at any point throughout the study without having to give a reason. Data will be retained for analysis from all participants after the point of consent and recruitment unless the participant specifically withdraws consent for their data to be used.

9.9. Schedule of Assessment

Event/Visit	Screening	Antenatal clinic	Labour
Inclusion/exclusion	x		
Informed consent		x	x
Medical history	x	x	x
Note review			x
Blood sample			x

9.10. End of Study Definition

The end of study is defined as the point when the last participant delivers her baby.

9.11. Subject withdrawal

All study participants are free to withdraw from the study at any time. All participant data will be included in the final analysis, unless a participant specifically asks for their data not to be included.

9.12. Data collection and follow-up for withdrawn subjects

Patients that withdraw consent or drop out before surgery will be replaced. The withdrawal will be documented in the CRF and medical records. Participants are not obliged to give the reason for withdrawing their consent, but we will attempt to ascertain trends (where possible) relating to study procedures in case this necessitates a protocol amendment.

10. Statistical considerations

10.1. Sample size

Based on the IL-1Ra Consortium score (Interleukin 1 Genetics, 2015), women with low IL-1Ra secretion associated with an allele score 0 comprise ~12% of the population. We hypothesise that these women are more likely to sustain ERMF or be prescribed antibiotics for >2 temperatures >37.5°C over a two-hour period, compared to women with higher IL-1Ra secretion (allele score ≥ 1). The overall incidence of ERMF in EPIFEVER was 13.4% (probably an underestimate with broader inclusion criteria and lower temperature threshold for antibiotic use, as per RCOG guidelines). If individuals with an allele score 0 are more likely to develop ERMF (~22%), compared with women with IL-1Ra allele scores ≥ 1 , at least 637 women will be

required to detect an absolute difference in primary outcome of ~13%, assuming 9% incidence in women with allele scores ≥ 1 ($\alpha=0.05$; $1-\beta=0.2$).

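### The group rates behind the sample size imply 10.6% overall fever incidence, below the 13.4% that the same paragraph calls probably too low, so the power at 637 women depends on which input is dropped

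*Protocol*

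**What the plan says.** Protocol section 10.1 (Sample size) gives all the inputs in one paragraph:

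- Share of women with score 0: "women with low IL-1Ra secretion associated with an allele score 0 comprise ~12% of the population".
- Incidence in that group: about 22%.
- Incidence in the rest: "assuming 9% incidence in women with allele scores ≥ 1".
- Target: the sample is the number "required to detect an absolute difference in primary outcome of ~13" percentage points.
- Size: "at least 637 women will be" needed, with α = 0.05. The power term is printed as 1−β = 0.2, read here as β = 0.2, that is, 80% power.
- Base rate: "The overall incidence of ERMF in EPIFEVER was 13.4% (probably an underestimate with broader inclusion criteria and lower temperature threshold for antibiotic use".

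Section 5.1 (Background) adds a general figure: "Epidural-related maternal fever (ERMF) occurs in 15-20% of labouring women". Section 10.2 confirms that the primary comparison is score 0 against score 1 or more.

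**The concern.** The two groups make up the whole cohort, so their rates, weighted by their shares, must average to the overall incidence. Here they do not. The paragraph quotes an overall rate, argues that the true one is probably higher, and then uses group rates that average to something lower.

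This paragraph is the only justification given for the size of the primary comparison. If the two groups do not differ significantly, readers will ask what difference 637 women could have shown. The answer should come from rates that agree with the protocol's own expected incidence.

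**Working it through.** **Inputs** (section 10.1): score-0 share 12%, rates 22% and 9%, overall 13.4%, N = 637. Assumed: two-sided α = 0.05, since the number of sides is not stated, and intended power 80%.

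**The plan's own figure.** The usual formulas for 22% vs 9% with a 12/88 split and 80% power give a total of 500 (pooled), 567 (continuity-corrected), 552 (arcsine) or 707 (unpooled). At 90% power, pooled gives 700. None reproduces 637, so the method behind it is unknown. That is a separate matter; the steps below take 637 as given.

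**Implied overall incidence.** 0.12 × 0.22 + 0.88 × 0.09 = 0.0264 + 0.0792 = 0.1056.

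**Can rounding close the gap?**
- Score-0 shares of 11% to 13% give 10.4% to 10.7%.
- Pushing all three inputs up by half a unit gives 0.125 × 0.225 + 0.875 × 0.095 = 11.1%.
- Rates of 22% and 9% average to 13.4% only if the score-0 share is (0.134 − 0.09) / 0.13 = 34%.
- Keeping 9% and the 12% share requires (0.134 − 0.88 × 0.09) / 0.12 = 45.7% in score 0.

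**Ways to reach 13.4%.**
- Keep 22%: the other rate is (0.134 − 0.12 × 0.22) / 0.88 = 12.2%, a difference of 9.8 points.
- Keep 13 points: the other rate is 0.134 − 0.12 × 0.13 = 11.8%, against 24.8%.
- Keep the risk ratio 22/9 = 2.44: the other rate is 0.134 / (0.12 × 2.44 + 0.88) = 11.4%, against 27.9%.

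**Power at 637.** Group sizes are n₀ = 0.12 × 637 = 76.4 and n₁ = 560.6. With difference d and overall rate p̄:

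- SE₀ = √[p̄(1−p̄)(1/n₀ + 1/n₁)]
- SE₁ = √[p₀(1−p₀)/n₀ + p₁(1−p₁)/n₁]
- Pooled power = Φ[(d − 1.96 SE₀)/SE₁]
- Unpooled power = Φ[d/SE₁ − 1.96]

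| Scenario | Rates | d | SE₀ | SE₁ | Pooled | Unpooled |
|---|---|---|---|---|---|---|
| As stated (10.6% overall) | 22% vs 9% | 0.130 | 0.0375 | 0.0489 | 88% | 76% |
| 13.4%, keep 22% | 22% vs 12.2% | 0.098 | 0.0415 | 0.0494 | 63% | 51% |
| 13.4%, keep 13 points | 24.8% vs 11.8% | 0.130 | 0.0415 | 0.0513 | 83% | 72% |
| 13.4%, keep risk ratio | 27.9% vs 11.4% | 0.165 | 0.0415 | 0.0530 | 94% | 87% |

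Fisher's exact test (76 vs 561) gives 86%, 58% and 80% for the first three rows. The pooled total for 80% power would be about 1,008 keeping 22%, 592 keeping 13 points and 375 keeping the risk ratio.

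**Minimum detectable difference.** Solving pooled power = 80% for d gives 11.3 points when the comparator is 9% and about 12.5 points when it is 12.2%.

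**Sensitivity to a higher incidence (pooled).**

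| Overall | Keep 22% | Keep 13 points | Keep risk ratio |
|---|---|---|---|
| 15% | 45% | 80% | 96% |
| 20% | 7% | 73% | over 99% |

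**The case against.** The strongest reply is that the stated target is a difference of about 13 points, and that target survives. At 13.4% overall with 13 points kept, pooled power is 83%, and at 15% it is still 80%. The detectable difference of about 12.5 points is inside the target. This stands. A reader might infer from the conflict that 637 women are too few; the documents do not support that, because the answer depends on which input is held and the protocol does not say.

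A reader might also infer that the low 9% comparator makes the detectable difference look larger. The reverse is true: a lower comparator makes the minimum detectable difference look smaller (11.3 against about 12.5 points). The 9% enlarges only the assumed effect, and only if 22% is held.

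The 7% power at 20% overall is not fair evidence alone. It holds score 0 at 22% against 19.7% in the rest, which gives up the study's hypothesis; the other two readings at 20% give 73% and over 99%.

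Finally, the 15-20% in section 5.1 carries no definition of fever. The primary endpoint in section 6.3 counts temperature from 4 hours after the epidural and/or antibiotics, and section 7.2 excludes women with established pyrexia. Whether 15-20% carries over cannot be judged from the protocol, so it serves only as a sensitivity range.

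Could those same features pull the incidence below 13.4%? Section 10.1 itself argues the other way, citing wider inclusion and a lower temperature threshold for antibiotics. The conflict with 13.4% therefore remains.

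**Conclusion.** The inputs are inconsistent: the group rates imply 10.6% overall, 2.8 points below an incidence that the same paragraph regards as probably too low. Rounding does not explain this and no other section does.

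The consequence for power is not settled. At 13.4% overall and 637 women it is about 63%, 83% or 94% (pooled), against about 88% on the stated rates. The choice of test matters as well: the unpooled calculation gives 76% on the stated rates and 72% with 13 points kept at 13.4%. The intended 80% is therefore not necessarily lost.

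These figures assume a two-sided 0.05 test, exactly 12% of women in score 0, and all 637 women contributing to the analysis. The point should be fixed, but it does not call the design, endpoint or comparison into question.

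**What to change.** Rewrite the sample size paragraph in section 10.1:

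1. State rates for score 0 and score 1 or more whose 12/88 weighted mean equals the expected overall incidence. Use 13.4% as the base case and 15-20% as a sensitivity range only. If a lower incidence is really expected, say so and give the reason.
2. Say which quantity is held as the overall rate changes: the score-0 rate, the 13-point difference or the risk ratio.
3. Restate the power, or the minimum detectable difference, at N = 637, naming the test and the number of sides. Correct the printed power term at the same time.

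Keep N at 637. Recruitment, endpoint and analysis are unaffected. The cost is one paragraph and possibly a less favourable stated figure.

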10.2. Method of analysis

For the primary clinical outcome, the relative incidence of the primary clinical endpoint will be compared between allele scores 0 versus ≥ 1 and across individual allele scores 0-4 inclusive. Significance will be set at $p<0.05$. For the laboratory measures in a subset of women in hospitals local to WHRI, ex-vivo IL-1Ra functionality in freshly obtained leucocytes will be assessed by flow cytometry and/or protein/gene transcription assays. For these studies, at least 26 samples are required to detect $\geq 25\%$ increase in IL-1Ra levels from control-treated samples for within-subject comparisons ($\alpha=0.05$; $1-\beta=0.9$).

Ethics

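### Protocol 10.1 prints the primary power as 20%; even read as 80%, the 637 women do not follow from the printed inputs

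*Protocol*

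**What the plan says.** Protocol section 10.1 gives the inputs to the primary sample size:

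- Score 0 group: "associated with an allele score 0 comprise ~12% of the population".
- Event rate at score 0: "If individuals with an allele score 0 are more likely to develop ERMF (~22" per cent).
- Event rate at score ≥ 1, with error rates: "assuming 9% incidence in women with allele scores ≥ 1 ($\alpha=0.05$; $1-\beta=0.2".
- Target: 637 women as a minimum, "required to detect an absolute difference in primary outcome of ~13" percentage points.

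Section 10.2 sets the comparison (the endpoint "will be compared between allele scores 0 versus ≥ 1 and across individual allele scores 0-4 inclusive") and the threshold ("Significance will be set at $p<0.05"). It names no test and no sidedness. The same section sizes the laboratory substudy with 1-β = 0.9. Section 9.12 says that women who withdraw or drop out are replaced. No section gives a loss rate.

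**The concern.** There are two linked problems.

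1. **The symbol.** 1-β is power. Section 10.1 therefore states 20% power for the only formally sized clinical hypothesis. Section 10.2 uses 1-β for power in the usual sense, so this is not a local convention in which 1-β means the type II error. No other section states a power for the primary comparison, so nothing elsewhere corrects it.
2. **The number.** The natural repair is to read β = 0.2. If 637 then followed from the printed inputs, the matter would end as a typing error. It does not follow, so correcting the symbol alone would leave a required minimum that a reader cannot check.

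At stake are the accuracy of the one power statement for the primary comparison, and whether a reader can tell what 637 was meant to achieve.

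**Working it through.** **Inputs** (section 10.1 unless noted)

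- f = 0.12 (share with score 0)
- p₀ = 0.22, p₁ = 0.09, d = 0.13
- α = 0.05. Two-sided is my assumption, as the protocol does not say.
- No loss allowance (none stated; section 9.12 replaces withdrawals)

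**Formulas for total N**

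- Mean rate: p̄ = 0.12 × 0.22 + 0.88 × 0.09 = 0.1056
- V₀ = p̄(1 − p̄) / [f(1 − f)] = 0.1056 × 0.8944 / 0.1056 = 0.8944
- V₁ = p₀(1 − p₀)/f + p₁(1 − p₁)/(1 − f) = 0.1716/0.12 + 0.0819/0.88 = 1.5231
- Pooled: N = (z_α√V₀ + z_β√V₁)² / d²
- Continuity-corrected: N_c = (N/4) × [1 + √(1 + 2/(N f(1 − f) d))]²
- Unpooled: N = (z_α + z_β)² V₁ / d²
- Arcsine: N = (z_α + z_β)² / [f(1 − f) h²], with h = 2 arcsin√0.22 − 2 arcsin√0.09 = 0.3670
- Fisher: exact enumeration of both binomials

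**Attempt to reproduce 637.** For 80% power (z_β = 0.8416):

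- Pooled: (1.96 × 0.9457 + 0.8416 × 1.2341)² / 0.0169 = 2.8923² / 0.0169 ≈ 495
- Continuity-corrected: (495/4) × (1 + √(1 + 2/6.795))² ≈ 566
- Unpooled: 7.849 × 1.5231 / 0.0169 ≈ 707
- Arcsine: 7.849 / (0.1056 × 0.1347) ≈ 552

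All two-sided results:

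| Method | N for 20% | N for 80% | N for 90% |
|---|---|---|---|
| Pooled | 39 | 495 | 698 |
| Fisher exact | – | about 540 | about 736 |
| Arcsine | 88 | 552 | 739 |
| Continuity-corrected | 99 | 566 | 769 |
| Unpooled | 113 | 707 | 947 |

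Fisher power is not monotone in N: at 80% it first crosses at 540 and settles by about 546. Rounding each group up moves the other totals by a few women (for example 501 instead of 495). No cell is 637. Against 80% power, 637 is above four of the methods by 142, 97, 85 and 71 women, and below the unpooled one by 70.

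**Power at 637.** 0.12 × 637 = 76.4, so 76 versus 561 women. The standard errors are 0.03755 (null, pooled) and 0.04903 (alternative).

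- Pooled chi-squared: Φ[(0.13 − 1.96 × 0.03755)/0.04903] = Φ(1.150) = 0.875
- Continuity-corrected: subtract ½(1/76 + 1/561) = 0.00747 from 0.13, giving Φ(0.998) = 0.841
- Fisher exact, by enumeration: 0.858
- Unpooled Wald: Φ(0.13/0.04903 − 1.96) = Φ(0.691) = 0.755 by approximation; 0.789 by exact enumeration

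**Could unstated choices explain 637?**

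- One-sided test at 90% power: 582 (pooled), 653 (continuity-corrected), about 658 (Fisher).
- Two-sided test at 85% power: 631 (arcsine), 652 (continuity-corrected).
- 80% power with a 10% loss allowance on the continuity-corrected figure: 566/0.90 = 629.
- Inputs moved within rounding, to 12.5%, 22.5% and 9%: 632 at 90% (pooled) or 641 at 80% (unpooled).

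Several come close. None is stated in the protocol and none gives 637 itself.

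**The case against.** The best defence is that 637 is of the right size and only the reporting is thin. The 12%, 22% and 13-point figures are all marked approximate, and small shifts in them, an 85% target or a modest loss allowance bring the answer near 637. The methods are also not unanimous: across all five, the 80% requirement runs from about 495 to 707, which brackets 637. The choice of test may sit in a statistical analysis plan that is not at hand.

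Much of this stands. It rules out calling 637 arbitrary, and the absence of a named test is not a finding in its own right. It does not remove the point. The protocol itself prints the power and prints it wrongly, so this is not something left to another document. The candidate explanations also differ in target power, sidedness and allowance, so a reader has to guess between them.

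Two stronger readings are tempting and should be resisted:

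- A reader might infer that the study was designed with 20% power, or is underpowered. The documents do not support this: 20% power would need only about 39 to 113 women.
- A reader might infer that a null result could not be interpreted. The rates, the split, α and N are all printed, so the delivered power can be computed, as above.

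**Conclusion.** The concern holds as a reporting error. The stated power of 20% is wrong, almost certainly a slip for β = 0.2, and 637 does not follow exactly from the printed inputs at 20%, 80% or 90% power under any of the standard two-sided methods tried.

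The practical harm is limited. On the protocol's own assumptions, 637 women give about 87% power (pooled chi-squared), 86% (Fisher) or 84% (continuity-corrected). Only an unpooled Wald test falls short of 80%, at 76% by approximation or 79% by enumeration.

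This rests on a two-sided test, a 12:88 split, rates of exactly 22% and 9%, and no losses. A one-sided test would raise the power at 637 to about 89% to 92% under the pooled, continuity-corrected and Fisher methods, but the protocol does not state one. The severity is should-fix.

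**What to change.** In section 10.1, replace the 1-β = 0.2 entry with the intended power, and state the test, the sidedness and any loss allowance that together lead to 637.

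If the original calculation cannot be recovered, say so. Then report the power that 637 delivers for the named primary test, for example about 87% for a two-sided chi-squared test with 76 versus 561 women, and drop the wording that makes 637 a required minimum. The test in that example is only an illustration, and the sponsor must name its own. A power worked back from N should not be presented as the original design target.

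The cost is one or two sentences in section 10.1. Enrolment, data collection and the planned comparison do not change.
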